Secondary Outcome Measures:	
 • Plasma and urinary catecholamines • Blood pressure and heart rate • Plasma sodium • Plasma renin activity
Statistical Considerations (sample size and analysis plan):	
Based on our preliminary findings of a standard deviation for urinary sodium excretion of 30 mEq/g creatinine, a sample size of 16/group (32 total) will have 80% power to detect a difference in group means (control vs. POTS) of 31 mEq/g creatinine with a 0.05 two-sided significance level. To allow for participant drop-out prior to study completion, we will plan to obtain informed consent from 35 participants in total.
 
Differences in urinary sodium in samples (1) collected at baseline vs. those collected following treatment (time effect) and (2) collected after placebo vs. carbidopa (treatment effect) will be assessed using a paired t-test and Wilcoxon signed-rank test. Differences between the patient and control groups (group effect) will be assessed using a student's t-test and a Mann-Whitney U test. Similar methods will be used to compare secondary outcome measures, such as BP, HR, plasma and urinary catecholamines, plasma renin activity, plasma aldosterone, and plasma sodium. All data analyses will be performed using SPSS 14.0 (SPSS, Chicago, IL) or STATA 8.2 (StataCorp, College Station, TX). All statistical tests will be two-sided. If these analyses indicate that the response to carbidopa differs between patients and controls, a mixed-effects model will be developed to describe the time, medication and group effects.

Sponsors (federal, state, foundation and industry support):	National Institutes of Health (NIH)

1.A. Protocol Overview

The purpose of the proposed research is to determine how changes in kidney dopamine (DA) activity influence urinary sodium excretion. Dopamine in the kidney plays an important role in maintaining sodium balance. We will decrease DA activity in the kidney by inhibiting DA synthesis via carbidopa administration. We will compare the active agent with a placebo. We also want to compare findings in normal volunteers and in patients with postural tachycardia syndrome (POTS). Some of these patients may not effectively regulate sodium excretion.

1.B. Dose Escalation Study of Carbidopa

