- After at least a 1 day washout period, the study will be repeated with Treatment B. Treatment B consists of exactly the same regimen as Treatment A. The participant will be randomized to receive placebo or carbidopa (whichever was not given during Treatment A).

Throughout the dosing period, participants will be monitored (HR and BP measurement, Psychiatric Symptom Questionnaire, and questioning by study personnel 2hr after each dose) for adverse events, including allergic reaction, nausea, worsening hypotension or tachycardia, arrhythmia, neuroleptic malignant syndrome, hallucinations or other psychiatric symptoms. No more doses will be given to a participant who experiences an allergic reaction, arrhythmia, increased body temperature $>100.4^{\circ}\text{F}$, or $>38^{\circ}\text{C}$, changes in supine BP $>20\text{mmHg}$ or changes in supine HR $>30\text{bpm}$, hallucinations or psychiatric symptoms (as determined by our Psychiatric Symptom Questionnaire). Adverse events and post-study changes in ECG or laboratory values (in relation to pre-study assessments) following carbidopa and placebo will be summarized for each cohort. Adverse events will be defined according to the Common Terminology Criteria for Adverse Events, version 4.0 (CTCAE). [REDACTED]

[REDACTED], the Independent Medical Monitor (IMM) for this study, will review the data and use clinical judgment to decide whether to proceed to the next higher dosage of the dose escalation study. In general, a grade 2 event in more than one participant or a grade 3 event judged to be drug-related in any one participant will lead to study termination. Post-dose laboratory assessments may be repeated to confirm abnormalities.

Participants in the dose escalation study will not be allowed to also participate in the main study.

1.C. Detailed Description of Main Study:

This study will only be conducted if the results of the dose escalation study indicate that the 200mg dosage of carbidopa is well tolerated when given every 6hr for 5 doses. We will determine whether inhibition of renal

dopamine formation by carbidopa administration leads to a decrease in urinary excretion of dopamine and sodium and whether the response differs in POTS and control populations. Carbidopa effects will be compared to those of a matching placebo, and the sequence of treatments (carbidopa before placebo or placebo before carbidopa) will be randomized.

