Previous findings by our research group suggest that mechanisms involved in orthostatic and absolute volume regulation contribute to POTS pathophysiology. We have preliminary data showing that patients with POTS do not decrease urinary sodium excretion after 30-60 minutes of upright posture, whereas healthy control participants do. We also reported that plasma renin activity (PRA) and aldosterone are paradoxically low in POTS in view of the reduced plasma volume. This indicates that sodium handling is perturbed in POTS. We therefore expect that patients with POTS may benefit from a reduction in urinary sodium excretion or that carbidopa-mediated changes in sodium excretion may differ between patients with POTS and healthy volunteers.

Hypothesis: In these studies, we will test the null hypothesis (H_0) that the effect of oral carbidopa administration on urinary sodium excretion will not differ between participants with POTS and healthy volunteers.

[figure not shown]
Research Question: Does orally administered carbidopa, by blocking the formation of renal dopamine from dopa, decrease urinary dopamine and sodium excretion in POTS and normal participants?

3. Background

Synthesis and degradation of catecholamines. The synthesis of catecholamines is summarized in Figure 1.

Tyrosine hydroxylase (TH) is the rate-limiting step in norepinephrine (NE) synthesis under almost all circumstances. NE acts as a feedback inhibitor of this enzyme. L-dopa (dopa) is the amino acid precursor of the endogenous

catecholamines and the immediate product of TH. L-Aromatic amino acid decarboxylase (AADC; also known as dopa decarboxylase or DDC) converts dopa to dopamine (DA) in both nonneuronal and neural tissues. Dopamine- β -hydroxylase (DBH), which converts DA to NE, is localized in vesicles of noradrenergic neurons in the central and peripheral nervous systems and in the adrenal medulla. Phenylethanolamine-N-methyltransferase (PNMT; NE to epinephrine (EPI)) is restricted to the adrenal medulla, the brain, and the heart, with only trace amounts in other locations.

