- At 2 hours after the last dose, participants will stand for 10 minutes for upright BP and HR measurements and collection of an upright blood sample, as described above. Participants will be asked to rate the severity of common orthostatic symptoms while supine and upright.
- Urine will be collected for two 4-hour periods after the last dose followed by a 16-hr collection to finish the 24-hour cycle for analysis of sodium, potassium, catecholamines, and creatinine.
- Participants may be discharged from the CRC approximately 8 hours after the last dose.
- After at least 24 hours, the protocol will be repeated with treatment B (Carbidopa 200 mg or placebo, whichever was not administered during treatment A). Depending on the interval, participants will either remain on the study diet or re-start the diet 2-3 days before admission for the 2nd phase.

4.H Schedule of Events-Main Study

Table 3 Study Schedule-Main Study

Dosing Regimen	Time of Dose	Monitoring/Labs
Predose	NA	24hr urine for catecholamines, sodium, potassium, creatinine to start 24hr prior to 1 st dose; supine and upright BP and HR; supine and upright plasma catecholamines, serum aldosterone, plasma renin activity; metabolic panel; start another urine collection over 24 hr for catecholamines, sodium, potassium, creatinine
Dose #1	0700	0900: supine BP and HR
Dose #2	1300	1500: supine BP and HR
Dose #3	1900	2100: supine BP and HR
Dose #4	0100	0300: supine BP and HR
Pre-Dose #5	0645	Supine and upright BP and HR; finish 24hr urine and start 4hr urine for catecholamines, sodium, potassium, creatinine
Dose #5	0700	0800: supine BP and HR; plasma catecholamines
		0900: supine and upright BP and HR; plasma carbidopa; Orthostatic Symptom Questionnaire; supine and upright plasma catecholamines, serum aldosterone, plasma renin activity
		1000: supine BP and HR; plasma catecholamines
		1100: supine BP and HR; metabolic panel; plasma catecholamines; plasma carbidopa; restart 4hr urine for catecholamines, sodium, potassium, creatinine
		1500: supine BP and HR; metabolic panel; plasma catecholamines; plasma carbidopa; start 16hr urine for catecholamines, sodium, potassium, creatinine

Table 4. Study Day Description-Main Study

Day	Treatment	Time	Obtain Consent	History & Physical	Pregnancy Test	Study Diet	Carbidopa or Placebo	Blood Draw	HR/BP	Urine
Pre-Study			X	X	X					
-3, -2					X					Start study diet
-1	0700				X					Start 24hr urine #1
1	0645				X			X	X	End & restart 24hr of urine collection

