Serious adverse events: The site investigator determines causality (definitely not related, probably not related, possibly related, probably related, definitely related) of the adverse event. The IMM will also review the SAE incident report.

The IMM may request further information if necessary and possibly suggest changes to the protocol or consent form to the NINDS as a consequence of adverse events. The Adverse Event Data Management System (AEDAMS) maintains audit trails and stores data (and data updated) and communication related to any adverse event in the study.

Non-serious expected adverse events: Except those listed above as immediately reportable, non-serious expected adverse events that are reported to or observed by the investigator or a member of his research team will be submitted to the DMCC in a timely fashion (within 20 working days). The events will be presented in tabular form and given to the IMM at least once every 12 months or as requested. Local site investigators are also required to fulfill all reporting requirements of their local institutions.

The DMCC will post aggregate reports of all adverse events (serious/not serious and expected, unexpected) for site investigators and IRBs.

5.F Study Discontinuation

The NIH and local IRB's (at their local site) have the authority to stop or suspend this trial at any time. This study may be suspended or closed:

- For safety concerns
- For other reasons as determined by the NIH or FDA

5.G Participant Discontinuation

An intent to treat approach will be used. All data acquired prior to termination for the reasons outlined below will be included in the primary analysis unless the participant withdraws consent. Every effort will be made to conduct a final study visit with the participant, and participants will be followed clinically until, if applicable, all adverse events resolve.

- Withdrawal of consent
- Withdrawal by the investigator
- Noncompliance to study diet and or urine collections
- Unanticipated reaction to study drug / placebo

5.H Data Quality and Monitoring Measures

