As much as possible data quality is assessed at the data entry point using intelligent on-line data entry via visual basic designed screen forms. Data element constraints, whether independent range and/or format limitations or 'relative' referential integrity limitations, can be enforced by all methods employed for data input. QA reports assess data quality post-data entry. As we note, data quality begins with the design of the data collection forms and procedures and incorporates reasonable checks to minimize transcription and omission errors. Of the more important quality assurance measures are the internal validity checks for reasonableness and consistency.

[figure not shown]
- Data Monitoring: The RDCRN DMCC identifies missing or unclear data and generates a data query to the consortium administrator contact.
- Data Delinquency Tracking: The Data Management and Coordinating Center will monitor data delinquency on an ongoing basis.

6. Statistical Considerations

Individual data will be reviewed for the Dose Escalation Study with the post-dose data compared to pre-dosing data. The data for each cohort will be summarized for review by [name] and the IMM of this study. The primary outcome is the urinary sodium concentration normalized to creatinine. Differences in urinary sodium in samples (1) collected at baseline vs. those collected following treatment (time effect) and (2) collected after placebo vs. carbidopa (treatment effect) will be assessed using a paired t-test and Wilcoxon signed-rank test. Differences between the patient and control groups (group effect) will be assessed using a student's t-test and a Mann-Whitney U test. Similar methods will be used to compare secondary outcome measures, such as BP, HR, plasma and urinary catecholamines, plasma renin activity, plasma aldosterone, and plasma sodium. All data analyses will be performed using SPSS 18.0 (SPSS, Chicago, IL) or STATA 8.2 (StataCorp, College Station, TX). All statistical tests will be two-sided. A mixed-effects model will be developed to describe the time, medication and group effects.

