Sample Size Calculation. Based on our preliminary findings of a standard deviation for urinary sodium excretion of 30 mEq/g creatinine, a sample size of 16/group (32 total) will have 80% power to detect a difference in group means (control vs. POTS) of 31 mEq/g creatinine with a 0.05 two-sided significance level. To allow for participant drop-out prior to study completion, we will plan to obtain informed consent from 35 participants in total (18 POTS, 17 healthy controls).

Randomization procedures were performed by [REDACTED] and the results provided to Vanderbilt's Investigational Pharmacy. Prior to admission, the pharmacy is notified whether the participant is a patient or healthy volunteer and the Investigational Pharmacist determines the treatment order (placebo or carbidopa first). At the end of the study, the blinding will be broken by the Vanderbilt Investigational Pharmacy and the order of agents will be revealed to the investigators and to the participants, if they so request.

7. Data Management

The investigators, research personnel and nursing staff at the CRC will collect the majority of the data at the bedside in real time. Data will be handwritten on CRFs provided by [name]. Routine labs are sent to

the hospital laboratory for analysis. Special study specific labs (ex: catecholamines) are sent to the GCRC Core Lab for analysis. Laboratory data will be obtained from Vanderbilt Medical Center's online medical chart system (StarPanel) and from the GCRC Core Laboratory website, both of which are password protected and only authorized personnel have access. After all data points have been retrieved, a member of the research team will enter the data into the DMCC database, which is also password protected and only accessible to authorized personnel. Data analysis will be performed routinely for periodic review. Hard copies of the CRFs will be maintained in the patient's research chart in a locked cabinet. Study participation will be complete following the inpatient evaluation. There will be no further study follow-up. Study records will be kept for at least 7 years following the publication or presentation of the data collected as part of this study.

All study data will be collected via systems created in collaboration with the RDCRN Data Management and Coordinating Center and will comply with all applicable guidelines regarding patient confidentiality and data integrity.

7.A Registration

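### The randomised crossover is analysed without a period term, and no single primary analysis is named that can use all the data section 5.G promises

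*Combined protocol and SAP*

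**What the plan says.** Section 1.C states that "the sequence of treatments (carbidopa before placebo or placebo before carbidopa) will be randomized", with a washout of at least one day before the second period. The null hypothesis in section 2 is that "the effect of oral carbidopa administration on urinary sodium excretion will not differ between participants with POTS and healthy volunteers".

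Section 6 says urinary sodium "collected after placebo vs. carbidopa (treatment effect) will be assessed using a paired t-test and Wilcoxon signed-rank test", and the synopsis says the same. Both use the term time effect for baseline versus post-treatment samples, not for period 1 versus period 2. POTS and controls are compared by Student's t-test and the Mann-Whitney test.

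On the model, section 6 says: "A mixed-effects model will be developed to describe the time, medication and group effects". The synopsis says: "If these analyses indicate that the response to carbidopa differs between patients and controls, a mixed-effects model will be developed". Neither place calls the model primary, and neither lists period or sequence.

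Section 5.G sets an intent-to-treat approach: "All data acquired prior to termination for the reasons outlined below will be included in the primary analysis", unless consent is withdrawn. The sample size paragraph adds: "To allow for participant drop-out prior to study completion, we will plan to obtain informed consent from 35 participants in total".

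**The concern.** Three things do not fit together.

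- **No period term.** In a crossover, a paired difference contains the treatment effect plus or minus any period shift, with the sign set by the sequence. If sequences are balanced, the shift cancels from the mean but stays in the variance, so power is lost. If they are unbalanced, part of it stays in the mean as bias. If the imbalance differs between POTS and controls, the bias falls on the contrast that is the stated null hypothesis.
- **Incomplete participants.** A paired test cannot use someone who has only one period, so it cannot deliver what 5.G promises. The mixed model could, but under the synopsis wording it is fitted only after a group difference in response has been seen.
- **No named primary analysis.** 5.G refers to one, but section 6 and the synopsis do not say which it is.

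A period shift is possible, not established. In Table 4 the diet starts on day -3 and there is no day 0. The baseline urine for Treatment A starts on day -1, after 2 days of diet. The one for Treatment B starts on day 4, after 6 days if the diet is not interrupted. Section 4.G also says that, depending on the interval, "participants will either remain on the study diet or re-start the diet 2-3 days before admission for the 2nd phase". Diet exposure before period 2 can therefore differ from period 1 and between participants, and the endpoint is urinary sodium.

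**Working it through.** **The plan's own figure.** From section 6: SD 30 mEq/g creatinine, difference 31, 16 per group, two-sided alpha 0.05. The two-sample t-test (noncentral t, 30 df) gives 80.7% power, which agrees with the stated 80%. This figure is for POTS versus control. The plan gives no power for carbidopa versus placebo.

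**Assumptions.** The documents give no period effect, no SD of the within-person difference and no sequence split. I take the SD of the difference as 30 and the period shift (period 2 minus period 1) as 0 to 30 mEq/g.

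**Model.** Carbidopa minus placebo equals the treatment effect plus the shift in one sequence and minus the shift in the other.

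- Balanced sequences: effective SD = √(30² + shift²), which is 31.6, 36.1 and 42.4 for shifts of 10, 20 and 30.
- Unbalanced sequences: bias = shift × (n₁ − n₂)/N.
- Period-adjusted estimate: the mean of the two sequence means, with SE = s·√[(1/n₁ + 1/n₂)/4]. At 8:8 this is 0.250s, the same multiple as for the paired test. At 10:6 it is 0.258s.

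**Balanced sequences (8:8 in each group).** Carbidopa versus placebo is shown for one group of 16 and a true effect of 22.5, where the paired test has 80% power with no shift.

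| Shift | POTS vs control, effect 31: closed form / simulated power | Paired t power | Paired t type I error |
|---|---|---|---|
| 0 | 80.7% / 80.6% | 80% | 5.0% |
| 10 | 76.5% / 77.4% | 77% | 3.9% |
| 20 | 65.3% / 67.0% | 66% | 2.0% |
| 30 | 51.6% / 50.3% | 49% | 0.6% |

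With a period term, power stays at about 81% for the group contrast and 80% for the one-group test at every shift, with type I error at 5%.

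**Unbalanced sequences (10:6 in a group of 16, shift 20).** Bias = 20 × (10 − 6)/16 = 5 mEq/g. Paired power is 85% or 43% depending on the direction of the shift, against 77% adjusted. The type I error of the paired test is 4.6%, so the harm here is in the estimate and in power.

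If the two groups split 10:6 in opposite directions, the group contrast is biased by 5 + 5 = 10 mEq/g and its type I error is 7.7%.

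The documents do not say whether order is blocked within group. If it is not, a split of 10:6 or worse in a group of 16 has probability 2 × 0.227 = 45%. Splits at least that uneven in opposite directions have probability 2 × 0.227² = 10%.

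**Incomplete participants.** Suppose all 35 − 32 = 3 extra participants supply period 1 only. Excluding them loses 4.4%, 3.3%, 2.3%, 1.1% or 0.5% of the information on the treatment effect, for within-person correlations of 0, 0.25, 0.5, 0.75 and 0.9.

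**The case against.** The strongest reply is that the design already limits period effects. Baseline collection starts only once sodium balance is reached on a fixed 200 mEq/day diet, and that urine is also used to check adherence. Extra diet days need not shift excretion once balance holds. A fresh 24-hour baseline precedes each treatment, so change scores could absorb a shift already present at baseline. This stands as a reason to expect a small shift. It does not settle the point, because the placebo-carbidopa contrast is not defined on changes from baseline.

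Second, the large losses need large shifts. A shift of 20 or 30 is two-thirds of the stated SD or equal to it. At 10 the group contrast loses 3 to 4 points, and at 5 its power is still 80%. Only one SD for the difference is shown here. All of this is fair, and the 50% figures should be read as the far end of a range.

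Third, the pharmacy is told whether the participant is a patient or a volunteer before order is set, which is compatible with separate balanced lists. Blocking is unknown, not absent. For the group contrast, type I error exceeds 5% only when the groups split in opposite directions: with 10:6 in one group only it is 3.2%, and with the same 10:6 split in both it is 2.0%. This also stands. Balance would remove the bias but not the loss of power.

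Fourth, the dropout element is small. That is correct: it is mainly an inconsistency with 5.G.

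**Conclusion.** The concern holds. The textual part is certain: no listed analysis contains period, the paired tests need both periods, the model's status differs between section 6 and the synopsis, and 5.G relies on a primary analysis that is never named.

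The numerical part is conditional on an unknown period shift and an assumed SD of 30 for the within-person difference. With no shift there is no harm. With balanced sequences the paired test stays unbiased and conservative, and a shift of 10 to 20 mEq/g takes about 3 to 15 points of power from either comparison. With unequal sequences the estimate is also biased, by a quarter of the shift at 10:6. The planned 16 per group is not affected. This should be fixed, because the remedy is cheap and uses data already collected.

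**What to change.** Name one primary analysis in section 6: a linear mixed model with fixed period, treatment, group and group-by-treatment and a random participant effect. Fit it to every participant with post-treatment data from at least one period, unless consent is withdrawn. For complete cases the period-adjusted crossover t-test is equivalent. State whether the outcome is the post-treatment value or the change from that period's baseline.

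Keep the paired t and Wilcoxon tests as supportive analyses. Remove the synopsis condition on fitting the model, so that the synopsis, section 6 and 5.G describe the same analysis. State whether treatment order is balanced within each group.

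A period term does not deal with carry-over. A first-period comparison, without a carry-over pre-test, can be added as a sensitivity analysis. It is optional and would have little power with about 8 participants per sequence in each group.

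The cost is wording and one degree of freedom, or two if the period effect may differ by group. With no period effect, power for the group contrast moves from 80.7% to 80.6% at 8:8. At 10:6 the one-group test goes from 80% to 77%. The pharmacy already holds the treatment order, so no new data are needed.

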8.F Importance of the knowledge to be gained	26
8.G Confidentiality	26
8.H Financial considerations	27
8.I Conflict of interest.....	27
9. References.....	28
10. Appendices	22
APPENDIX 1a: Sample Informed Consent Form- POTS	30
APPENDIX 1b: Sample Informed Consent Form – Healthy Volunteer	36
APPENDIX 1c: Sample Informed Consent - Dose Escalation - POTS.....	42
APPENDIX 1d: Sample Informed Consent - Dose Escalation - Health Volunteer.....	48

1. Synopsis

Protocol Number:	ARD6101
Protocol Title:	Peripheral Dopamine after Carbidopa Administration in Postural Tachycardia Syndrome
Study Chair:	[name] and [name]
Statistician:	[REDACTED]
Consortium:	Autonomic Rare Diseases Clinical Research Consortium
Participating Sites:	Vanderbilt University Medical Center
Activated by Vanderbilt, Date:	May 2008
Activated by RDCRN, Date:	April 2011
Sample Size:	16/group (32 total for participants with POTS and healthy controls) To allow for participant drop-out prior to study completion, we will plan to obtain informed consent from 35 participants in total (18 POTS, 17 Controls).
Target Enrollment Period:	5 yr
Study Design:	Randomized, double-blind, placebo-controlled crossover
Primary Study Objective:	The purpose of the proposed research is to determine how changes in kidney dopamine (DA) activity influence urinary sodium excretion. Dopamine in the kidney plays an important role in maintaining sodium balance. We will decrease DA activity in the kidney by inhibiting DA synthesis via carbidopa administration. We will compare urinary sodium excretion following the active agent and a placebo in participants with POTS and healthy controls. Urinary and plasma catecholamines will be measured to assess changes produced by carbidopa treatment. A dose escalation study with doses of 50mg, 100mg and 200mg will first be conducted to assess how well these doses are tolerated when given every 6 hours.
Secondary Study Objective:	We also want to compare findings in normal volunteers and in participants with postural tachycardia syndrome (POTS). These patients are characterized by an excessive increase in heart rate with standing. To determine whether some of these patients do not effectively regulate sodium excretion, the catecholamine, diuretic, and cardiovascular responses following orally administered carbidopa in participants with POTS will be compared with those of healthy volunteers. The dose escalation study will therefore include both POTS and controls.

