		1100: supine BP and HR; metabolic panel; plasma catecholamines; plasma carbidopa; restart 4hr urine for catecholamines, sodium, potassium, creatinine
		1500: supine BP and HR; metabolic panel; plasma catecholamines; plasma carbidopa; start 16hr urine for catecholamines, sodium, potassium, creatinine

Table 2. Study Day Description-Dose Escalation

3

Day	Treatment	Time	Assessments for Tolerability	Obtain Consent	History & Physical	Pregnancy Test	Study Diet	Carbidopa or Placebo	Blood Draw	HR/BP	Urine
Pre-Study			X	X	X	X			X		
-3, -2						X					Start study diet
-1	0700					X					Start 24hr urine #1
1	0645					X			X	X	End & restart 24hr urine
	A 0700, 1300, 1900					X	Doses 1, 2, 3				Continue 24hr urine #2
	0900, 1500, 2100	X				X			X	X	Continue 24hr urine #2
2	0100					X	Dose 4				Continue 24hr urine #2
	0300	X				X			X	X	Continue 24hr urine #2
	0645-0700					X	Dose 5		X		End 24hr, start 4hr urine #1
	0800					X			X	X	Continue 4hr urine #1
	0900	X				X			X	X	Continue 4hr urine #1
	1000					X			X	X	Continue 4hr urine #1
	1100					X			X	X	End 4hr urine #1 & start 4hr urine #2
May be discharged	1500					X			X	X	End 4hr urine #2 & start 16hr
3(washout day)	0700					X					End 16hr urine
4	0700					X					Start 24hr urine
5	0645					X			X	X	End & restart 24hr urine
	B 0700, 1300, 1900					X	Doses 1, 2, 3				Continue 24hr urine #2
	0900, 1500, 2100	X				X			X	X	Continue 24hr urine #2
6	0100					X	Dose 4				Continue 24hr urine #2
	0300	X				X			X	X	Continue 24hr urine #2
	0645-0700					X	Dose 5		X		End 24hr, start 4hr urine #1
	0800					X			X	X	Continue 4hr urine #1
	0900	X				X			X	X	Continue 4hr urine #1
	1000					X			X	X	Continue 4hr urine #1
	1100					X			X	X	End 4hr urine #1 & start 4hr urine #2
	1500					X			X	X	End 4hr urine #2 & start 16hr
7	0700										End 16hr urine

4.G Data Elements-Main Study

- A minimum of 9 days is needed to complete the study with 2 nights on the CRC for the active compound and 2 nights for the placebo.
- Participants will be provided a 200 mEq/day sodium diet, free of methylxanthines and low in monoamines, by the kitchen of the Clinical Research Center (CRC).
- After achieving sodium balance on the study diet over 2-3 days, participants will collect urine over 24hr starting at 0700hr, for baseline assessment of sodium, potassium and catecholamines and to confirm adherence to the study diet.
- Participants will be admitted to the CRC that afternoon or evening.

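### Each crossover period has its own pre-dose urine sodium/creatinine, but no planned test or model names it as a covariate, so precision may be forgone

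*Combined protocol and SAP*

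**What the plan says.** The design is "Randomized, double-blind, placebo-controlled crossover" in two groups, POTS and healthy controls. Section 6 states: "The primary outcome is the urinary sodium concentration normalized to creatinine".

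Baseline collection is in Section 4.G: "participants will collect urine over 24hr starting at 0700hr, for baseline assessment of sodium, potassium and catecholamines". Table 3 adds creatinine to the assays on that urine, so the primary outcome itself exists at baseline. The procedure is repeated for Treatment B, and Table 4 starts a new 24-hour urine on Day 4, before the Day 5 dose. Each period therefore has its own baseline.

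The interval between periods is at least 24 hours, with no upper limit. Depending on its length, "participants will either remain on the study diet or re-start the diet 2-3 days before admission for the 2nd phase".

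Section 6 (and the Synopsis) uses these data as follows:
- **Treatment effect:** samples "collected after placebo vs. carbidopa (treatment effect) will be assessed using a paired t-test and Wilcoxon signed-rank test".
- **Group effect:** Student's t and Mann-Whitney tests; the variable compared is not named.
- **Time effect:** a separate paired test of baseline against post-treatment samples.
- **Mixed-effects model** for time, medication and group: planned outright in Section 6, but in the Synopsis only if the simple tests suggest that the response differs between groups. No baseline covariate, period term or sequence term is named in either place.

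**The concern.** In a crossover, stable differences between people cancel in the carbidopa-minus-placebo difference. What remains includes any difference in the state from which a person began each period. Here that state is sodium balance, and it can differ between periods: the gap is open-ended, the diet may be stopped and restarted, and the diet days before admission are spent outside the Clinical Research Center. The trial measures this state before each period but does not carry it into the treatment or group test.

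At stake is the precision of the carbidopa effect, and of its difference between POTS and controls, which is the null hypothesis in Section 2. With 16 people per group, a moderate cut in residual variance would be useful, and the data for it are already being collected.

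**Working it through.** **1. The plan's own figure.** Inputs from the sample size paragraph of Section 6: "standard deviation for urinary sodium excretion of 30 mEq/g creatinine"; "80% power to detect a difference in group means (control vs. POTS) of 31 mEq/g creatinine"; "with a 0.05 two-sided significance level"; 16 per group.
- Normal approximation: n = 2 × (1.96 + 0.84)² × 30² / 31² = 14.7, so 15 per group.
- Two-sample t-test (noncentral t): power is 78.0% at 15 per group and 80.7% at 16.

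The stated 16 per group reproduces without any gain from baseline.

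**2. Effect of the covariate.** For each person let D = outcome on carbidopa minus outcome on placebo, and B = baseline before carbidopa minus baseline before placebo. Let r be the correlation of D with B. Regressing D on B multiplies the residual variance by (1 − r²). In the two-group model the residual degrees of freedom fall from 30 to 29, so the factor is about (1 − r²) × 30/29. The documents give no value for r; the range is assumed.

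| r | Factor | Equivalent n = 32 / factor |
|---|---|---|
| 0 | 1.000 × 1.034 = 1.03 | 30.9 |
| 0.3 | 0.91 × 1.034 = 0.94 | 34.0 |
| 0.5 | 0.75 × 1.034 = 0.78 | 41.2 |
| 0.7 | 0.51 × 1.034 = 0.53 | 60.7 |

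Break-even is at r² = 1/30, so r is about 0.18.

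**3. Power for the group difference in carbidopa effect.** I simulated 16 per group with a true group difference in D of 31 and an SD of D of 30. That SD is an assumption; the protocol does not say that its 30 refers to D. Unadjusted power is about 81%. With B as covariate it is about 79%, 83%, 89% and 97% at r = 0, 0.3, 0.5 and 0.7. Adding a sequence indicator changes these by less than one percentage point.

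**4. What r depends on.** Take equal variances, a correlation rw between baseline and outcome in the same period, and a common correlation rb between measurements from different periods. Then r = (rw − rb) / (1 − rb).
- rw = rb gives r = 0: no gain.
- rb = 0.5, rw = 0.6 gives r = 0.2 and a factor of 0.96 × 1.034 = 0.99.
- rb = 0.5, rw = 0.7 gives r = 0.4 and a factor of 0.84 × 1.034 = 0.87.
- With rb = 0.5, reaching r = 0.5 or 0.7 needs rw = 0.75 or 0.85.

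**5. Why a covariate and not a change score.** Subtracting each period's baseline multiplies the variance of D by 2(1 − rw)/(1 − rb) = 2(1 − r): 2.0 at r = 0, 1.4 at r = 0.3, 1.0 at r = 0.5 and 0.6 at r = 0.7. It doubles the variance when baseline carries no period-specific information.

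**6. If the paired test is run within one group (n = 16).** Section 6 does not say whether it pools the groups. The allowance for estimating one slope is then 1 + 1/13 = 1.077. At r = 0.3 the factor is 0.91 × 1.077 = 0.98; break-even is at r² = 1/14, r about 0.27.

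**The case against.** The strongest case against is that no loss has been shown. Pairing already removes stable between-person variance. The design also limits drift between periods: the research kitchen supplies a fixed 200 mEq/day sodium diet, the baseline urine follows two to three days on it and doubles as a check that it was kept, an interrupted diet is restarted before period 2, and dietary noncompliance is listed under participant discontinuation. The correlation r could therefore be near zero. This stands, and it is why the gain can be given only as a range.

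Second, baseline is not ignored altogether. It feeds the time-effect test, and it may enter the mixed model as a level of time. That also stands. But the model names no baseline covariate, and whether it is conditional differs between the Synopsis and Section 6, so it does not settle the matter.

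Third, the Day 4 baseline comes after Treatment A, possibly with only one washout day. If Treatment A still affects sodium balance on Day 4 but no longer does when the outcome is collected, adjustment would shift the estimate. This is a fair caution. It calls for an unadjusted analysis alongside the adjusted one, not for leaving the covariate out.

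Fourth, the baseline covers 24 hours while some post-dose collections cover 4 or 16. A covariate need not match the outcome in length; a mismatch would tend only to lower r.

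A reader might go further and infer that the planned tests are wrong, or that the trial is mis-sized. Neither follows. The unadjusted tests are not made invalid by lacking a covariate, and the sample size reproduces without one. A reader might also apply an ordinary baseline adjustment to the group comparison of raw values, where power would rise to between 84% and 98% for correlations of 0.3 to 0.7. The documents do not support that reading either: Section 6 does not say that raw values are compared, the stated hypothesis concerns the difference in carbidopa effect, and the groups are not randomized, so adjusting raw values would change the question.

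**Conclusion.** This is a cheap improvement, not an error. Both period baselines are collected on the primary outcome, and neither the treatment test, the group test nor the mixed model names them as a covariate. Adjustment could cost about 3% of variance (r = 0) or cut it by about 6%, 22% or 47% (r = 0.3, 0.5 or 0.7) with 32 participants. These figures rest on an assumed r, on a linear relation, and on no material carry-over into the Day 4 baseline. That precision is definitely being lost cannot be concluded from the documents. The case for acting is that the downside is small and bounded, apart from carry-over, and that the choice is best fixed before unblinding.

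**What to change.** In Section 6, prespecify a regression of each person's carbidopa-minus-placebo difference in urinary sodium/creatinine on that person's baseline difference (before carbidopa minus before placebo), with group and a treatment-sequence indicator. In a regression of differences, the sequence indicator carries the period effect. The group coefficient then tests the Section 2 hypothesis; with group and sequence centred, the intercept estimates the carbidopa effect. An equivalent mixed model would serve, provided that it is unconditional in both the Synopsis and Section 6 and uses baseline as a covariate, not as a change score. State which post-treatment urine collection is the outcome.

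Keep the unadjusted paired t, Wilcoxon, two-sample t and Mann-Whitney tests as sensitivity analyses. A marked difference between adjusted and unadjusted estimates would help reveal carry-over into the Day 4 baseline, or undue influence of a poor urine collection.

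Cost: a few sentences, no new data or procedures, one degree of freedom for the covariate (about 3% of variance if r = 0) and one more for the sequence term.
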